Baseline demographics and non-efficacy outcomes, including retention, frequency of adverse events, and receipt of the first injection of naltrexone-xr will be tabulated and summarized for this open-label treatment group using means, standard deviations and percentages where appropriate. Opioid use (Timeline Follow-Back), craving for opioids (VAS scale), urine toxicology, and depression scores (HAMD) during detoxification and post detoxification will also be analyzed using similar models as in the primary hypothesis. PROC GLIMMIX in SAS® 9.4 will be used to conduct all analyses. All statistical tests will be two-sided with a level of significance of 5%.

Hypotheses testing:

Primary Hypothesis: Lofexidine will be associated with reduced symptoms of opioid withdrawal during the 2-10 days induction phase as compared to baseline (day 1).

To analyze the primary hypothesis, withdrawal severity (COWS) during the 2-10 days induction phase will be summarized using descriptive summaries and analyzed using longitudinal generalized linear mixed effects models with a main effect of time, adjusted by the baseline (day 1) withdrawal score. Based on the distribution of the outcome corresponding link function will be used (eg. log for skewed data etc). A random intercept will be used to account for the between subject variances and an autoregressive (AR1) covariance structure to account for the correlation of the repeated observations within subjects over time.

Secondary Hypotheses: Lofexidine used to manage opioid withdrawal symptoms will result in successful initiation of outpatient naltrexone-XR treatment by the completion of the induction phase and patients receiving first naltrexone-xr injection.

To analyze the secondary hypothesis, the proportion of subjects who complete the induction phase and receive the first naltrexone-xr injection will be calculated. A one-sample proportion test will be used to compare whether the sample proportion is significantly different from benchmark proportions of successful induction to naltrexone-xr. Additionally, 95% confidence interval will be computed to estimate the expected range of population proportion of successful induction.

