Aim 1: To evaluate the safety and tolerability of lofexidine using standard dosing in the management of opioid withdrawal symptoms while initiating outpatient treatment with naltrexone.

Description of Subject Population

Sample #1

Specify subject population

Adults with current Opioid Use Disorder

Number of completers required to accomplish study aims

10

Projected number of subjects who will be enrolled to obtain required number of completers

20

Age range of subject population

18-60

Gender, Racial and Ethnic Breakdown

Both males and females will be recruited. All eligible subjects are accepted; however past experience with recruitment for other studies in this population suggest that the sample will be 75% male, 55% Caucasian, 30% Hispanic-American, 10% African-American, and 5% other minorities based on data from previous trials.

Description of subject population

Prospective participants must be adult (18 to 60 years of age) and meet criteria for current opioid use disorder by history and urine toxicology. Other substance use diagnoses are not exclusionary since multiple substance abuse is common in this population, and such an exclusion would rule out a large proportion of the population and limit the generalizability of the study. However, physiological dependence on alcohol or sedative-hypnotics with impending withdrawal is exclusionary. Maintenance on methadone or other long-acting agonist (e.g. buprenorphine) is exclusionary. Prospective participants cannot have concurrent psychiatric or medical conditions that would interfere with participation (e.g. mania, psychosis, pregnancy or failure to use adequate contraception).

Recruitment Procedures

Describe settings where recruitment will occur

All screening and study procedures will occur at the Substance Treatment and Research Services (STARS) of the Division on Substance Abuse (STARS Downtown) situated on [name].

How and by whom will subjects be approached and/or recruited?

Screening for this study will be covered by the Substance Treatment and Research Service (STARS) umbrella screening protocol #6582R (PI: [name]). Trained research assistants and administrative assistants under the supervision of the principal investigator conduct the initial phone screening. Under protocol #6582R, patients who contact STARS interested in research trial participation are informed that

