Indicate which of the following are employed as a part of screening or main study consent procedures

✓ Consent Form

Persons designated to discuss and document consent

Select the names of persons designated to obtain consent/assent

- [name]
- [name], MD
- [name]
- [name]
- [name], MD
- [name], MD
- [name], MD
- [name], MD
- [name]. MD
- [name]
- [name], MD

Type in the name(s) not found in the above list

Study Procedures

Describe the procedures required for this study

Potential subjects will undergo a screening visit which will include a demographics questionnaire, medical history, physical examination, psychiatric evaluation, laboratory testing, and electrocardiogram. The MINI International Neuropsychiatric Interview (MINI) will be conducted to determine current DSM-5 diagnoses. Eligible participants will be offered the opportunity to participate in the research treatment study, using the IRB-approved consent form obtained by the research psychiatrist.

This is an open-label pilot trial to evaluate the safety and tolerability of lofexidine in the management of opioid withdrawal symptoms while initiating outpatient treatment with naltrexone. The initiation procedure will be a flexible detoxification lasting 2 to 10 days concluding with the injection of XR-Naltrexone (Vivitrol). Lofexidine will be fixed-flexible dosing started on day 1 with maximum dose being three 0.18mg tablets taken orally 4 times daily at approximately 4-to 6-hour intervals. Lofexidine treatment will continue throughout the detoxification, up to 10 days, and will be discontinued with a gradual dose reduction over 2 to 4 days (Table 2). Precipitated withdrawal symptoms are treated with lofexidine, clonazepam, and other adjuvant medications as detailed below.

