This outpatient detoxification/naltrexone induction medication protocol is outlined in Table 2, below. Evaluation of withdrawal severity (COWS) and vital signs, will be obtained at least twice per day (at the beginning and end of their study visit). Additional COWS can be administered as per clinical judgment of the study physician and nurse practitioner.

For female participants, a urine pregnancy test will be obtained on the day of each vivitrol administration. If at any time during the study a female participant has a positive urine pregnancy test, this will be reported to the IRB and the study sponsor, US WorldMeds and the participant will be discontinued from the study. We will follow our study discontinuation procedure as outlined below to transition these individuals to a treatment program in the community.

Outpatient Treatment Post-Detoxification

Study Visits

Participants will have two weekly clinic visits during the first month of treatment and one weekly visit during the second month. At each visit the patient meets with the research assistant to complete research ratings, including self-report of withdrawal, mood, and drug use. The patient provides a urine sample under observation by a staff member at each visit. The sample is tested immediately for opioids. Vital signs are also taken. Once a week participant will meet with a study psychiatrist for safety and tolerability evaluation, along with medical management therapy.

Participants may come to the clinic to be seen as frequently as needed. In particular, any participant who is experiencing protracted opioid withdrawal will be offered clinical contact on a frequent, even daily, basis. For clinical matters arising in the evenings or on weekends, participants will have access to the 24-hour emergency telephone service, staffed by physicians familiar with this protocol who can address patients' concerns.

Outpatient medications

On the day after the XR-naltrexone injection participants will receive tapering doses of lofexidine for 2-4 days. During the subsequent 8-week course of outpatient treatment, patients receive additional injection of Vivitrol 380 mg, at week 4.

Medication Management

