Buprenorphine has been associated with adverse effects typical of opioid agonist drugs (e.g. sedation, constipation, insomnia, headache, nausea), although as a partial agonist such effects are typically less pronounced than they would be with a full agonist. The most common adverse event associated with the sublingual administration is oral hypoesthesia. Other adverse events were constipation, headache, intoxication, disturbance in attention, palpitations, insomnia, sweating, and blurred vision. Buprenorphine by itself has little tendency to suppress respiration and is associated with a low risk of overdose, a safety advantage. However, there is a risk of overdose if buprenorphine is combined with sedative drugs such as benzodiazepines or alcohol, analogous to the risk of combining such sedating medications with a full agonist like methadone. As a partial agonist, buprenorphine can precipitate an acute opioid withdrawal reaction if taken within 12-18 hours of another short-acting full opioid agonist, or within 48-72 hours of a longer-acting full opioid such as methadone. Study physicians have extensive experience, in both research and clinical settings, in administering buprenorphine and in the management of opioid withdrawal symptoms.

Side Effects of Extended-Release (XR), Injectable Naltrexone: The most common side effect associated with injectable naltrexone is injection site reaction. XR-naltrexone is administered as a gluteal intramuscular injection and injection site reactions, mostly pain, and occur in approximately 5% of patients in opioid treatment studies. These reactions are generally mild and include pain, tenderness, indurations, bruising, pruritus and swelling. Generally, these reactions last 1-3 days. Rare skin reactions at the site of the injection have been reported, including sterile abscesses, which may relate to inadvertent injection into fatty tissue, rather than muscle. Patients will be informed of this risk, and baseline physical evaluation will include examination of the buttock for excessive adiposity. If a patient is examined by a physician and found to have an abscess, necrosis, cellulitis or extensive swelling, an appropriate surgical referral will be made. In addition, Vivitrol could result in withdrawal symptoms at the first dose. Study physicians will inform participants of this risk prior to receiving the injection.

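### Lofexidine safety is the sole aim, but the lead analysis is a single-group COWS change, and the adverse event frequency has no on-lofexidine window and no interval

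*Combined protocol and SAP*

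**What the plan says.** **Aim.** Specific Aims and Hypotheses lists a single aim: "To evaluate the safety and tolerability of lofexidine using standard dosing in the management of opioid withdrawal symptoms", in the setting of starting outpatient naltrexone. Study Procedures gives the same purpose: "This is an open-label pilot trial to evaluate the safety and tolerability of lofexidine in the management of opioid withdrawal symptoms". The Lay Summary and the Background repeat it.

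**Hypotheses.** The Overview of Data Analytic Plan states as primary: "Lofexidine will be associated with reduced symptoms of opioid withdrawal during the 2-10 days induction phase as compared to baseline (day 1". It is tested as a time effect in a mixed model for COWS in one open-label group. The secondary hypothesis is completed induction with a first XR-naltrexone injection, compared with benchmark proportions. For that outcome the plan adds: "Additionally, 95% confidence interval will be computed to estimate the expected range of population proportion of successful induction".

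**Safety analysis.** The plan says that baseline demographics and "non-efficacy outcomes, including retention, frequency of adverse events, and receipt of the first injection of naltrexone-xr will be tabulated and summarized", using means, standard deviations and percentages. It says nothing more about adverse events.

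**Exposure.** Lofexidine is given through a detoxification of 2 to 10 days. The Outpatient medications section then says: "On the day after the XR-naltrexone injection participants will receive tapering doses of lofexidine for 2-4 days". On XR-naltrexone, the risk section says: "The most common side effect associated with injectable naltrexone is injection site reaction". It adds: "Generally, these reactions last 1-3 days".

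**Data collection.** Reporting of Adverse Events requires onset time, duration, severity and suspected relationship to study drug for each event. The SAFTEE description adds the action taken.

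**The concern.** The aim and the analysis hierarchy point to different questions. A change in COWS over time in one uncontrolled group says little about whether lofexidine is safe or tolerated. Participants start lofexidine and are told to stop opioids on the same day, and they also receive clonazepam and zolpidem. No hypothesis or defined lead outcome concerns safety.

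The safety item that remains does not say over which period events are counted. A frequency over all follow-up would satisfy the wording, yet would combine events on lofexidine with events that arise later under XR-naltrexone alone. The window could then be chosen after the data are seen. The plan computes an interval for the induction proportion but none for the outcome named in the aim. It also does not name, as outcomes, the events for which the protocol itself withholds lofexidine.

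**Working it through.** 1. **Planned numbers** (Description of Subject Population): 10 completers from 20 enrolled, so 10/20 = 50% completion is implied. The documents give no event rate, effect size, SD or precision target, so there is no stated safety precision to reproduce.

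2. **Days on lofexidine, inducted participant** (Study Procedures; Outpatient medications): detoxification days + taper days. Shortest: 2 + 2 = 4. Longest: 10 + 4 = 14.

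3. **Follow-up after detoxification** (Study Procedures): 4 weeks of two visits plus 4 weeks of one visit = 8 + 4 = 12 visits over 8 weeks. The end-of-study visit makes 13. The payment figures agree: 13 x $20 = $260, 10 x $20 = $200, total $460, as in the Compensation section. Follow-up is therefore about 8 weeks plus a closing visit, with a second XR-naltrexone injection at week 4.

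4. **Overlap of the two drugs.** The taper begins the day after the injection. Share of lofexidine days after injection = taper/(detoxification + taper):
   - lowest, 10-day detoxification and 2-day taper: 2/12 = 16.7%
   - highest, 2-day detoxification and 4-day taper: 4/6 = 66.7%

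   So even a correct on-lofexidine window covers both drugs in part, unless it is split at the injection.

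5. **Precision of an adverse event proportion.** Exact (Clopper-Pearson) 95% limits for x of n: lower = 2.5% quantile of Beta(x, n - x + 1); upper = 97.5% quantile of Beta(x + 1, n - x). For x = 0 the upper limit is 1 - 0.025^(1/n). The counts are illustrative assumptions, not figures from the documents.
   - 0/20: 1 - 0.025^(1/20) = 16.8%, so 0-16.8%
   - 4/20: 5.7-43.7%
   - 0/10: 1 - 0.025^(1/10) = 30.8%, so 0-30.8%

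   The 0/10 line shows what a completers-only denominator would cost. It also applies after the injection if only 10 are injected. The documents do not give that number; 10 to 20 is assumed.

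**The case against.** The strongest reply is that this is a small pilot with a plan titled as an overview. Descriptive adverse event counts are ordinary at this size, no adverse event test is planned, and anyone given n/N can compute an interval. The plan also tabulates retention and receipt of the first injection, which bear on how well the procedure is tolerated, and on the page the adverse event sentence comes before the primary hypothesis. All of this is fair. It does not supply a window, which a reader cannot rebuild from a whole-study count, and it does not change which hypothesis is labelled primary.

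Four stronger readings are tempting, and the documents do not support them:

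- *Most reported events would fall off lofexidine, because most days do.* Calendar days are not events. Contact is daily during detoxification and sparser later: with the longest detoxification, 10 of 23 visits (43%) fall in it; with the shortest, 2 of 15 (13%). Lofexidine effects such as hypotension may cluster on drug.
- *The analysis population is undefined.* There is one arm, dosed on Day 1 after consent. Only a completers-only denominator needs ruling out.
- *Follow-up is stated inconsistently as 8 and 9 weeks.* The visit count in the working reconciles the two.
- *Safety data are not properly collected.* Onset, severity, action taken and suspected relationship are recorded. The gap is in the analysis.

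The overlap at the injection should not be overstated either. Site reactions occur in about 5% of patients, so 0.5 to 1 participant among 10 to 20 injected, and they are recognisable by term. A table by term would separate most events of the two drugs. That supports a by-term table; it does not remove the need for a window.

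**Conclusion.** The point holds and should be corrected, though it does not undermine the trial. Followed as written, the lead result would not answer Aim 1, and the only safety result could be a whole-study frequency that does not describe the roughly 4 to 14 days on lofexidine. The missing interval is secondary to this, but it is inconsistent with the interval planned for induction.

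If all 20 enrolled are dosed, no affected participants would still leave an upper 95% limit of 16.8%, and 4 of 20 would give 5.7-43.7%. The trial can therefore support estimation with wide limits, and the plan should say so. The conclusion assumes that the two attachments not shown, the medication flow chart and the assessment table, do not define an analysis window; the data analytic plan refers to neither for adverse events.

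**What to change.** Reconcile the analysis plan with Aim 1. Make safety and tolerability the lead analysis, as estimation, with the COWS model supporting; or amend the aim so that COWS leads. In either case, in all participants who took at least one lofexidine dose, report n/N with an exact 95% CI for:

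- (a) any adverse event with onset from first to last lofexidine dose, also tabulated by term and split at the XR-naltrexone injection, with those injected as the denominator after it;
- (b) any lofexidine dose hold under the criteria in Study Procedures (dizziness or lightheadedness, low blood pressure, orthostatic change);
- (c) lofexidine stopped because of an adverse event.

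List later adverse events separately. State in advance in which period events just after the last dose count, since rebound hypertension is among the listed lofexidine risks. Tabulate relatedness, descriptively, only if the form shows which drug is meant by study drug. State that on-lofexidine events are not attributed to lofexidine, because clonazepam, zolpidem and the naloxone challenge fall in the same period.

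The cost is plan wording and a few table rows. Onset and action taken are already collected. Holds must be logged as such; the text shown names no separate field for them. The downside is a lead result that is an estimate with a wide interval and not a p-value.

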However, one of the main barriers to initiating XR-naltrexone in active opioid users is the need for a 7 to 10-day abstinence from opioids prior to the first dose (Vivitrol, Package Insert). This means that individuals wishing to start XR-naltrexone first need to undergo detoxification, usually including 4-7 days of a buprenorphine or methadone taper, followed by 7-10 days of an opioid “washout.” Unfortunately, many find this extended wait period difficult, due to persisting withdrawal symptoms and cravings, and are unable to complete it.

We previously demonstrated that transition from active opioid use (heroin or prescription opioid) to XR-naltrexone could be achieved in 7 days on an outpatient basis, using a regimen of buprenorphine, clonidine and other ancillary medications, and gradual up-titration of oral naltrexone beginning with very low doses (Sullivan et.al; 2016). Further shortening the delay to first XR-naltrexone administration, may enable more patients to successfully initiate treatment. However, a shorter procedure may produce more severe withdrawal symptoms. The use of clonidine in the management of opioid withdrawal in previous trials was found to be effective in relieving symptoms, but dosing was limited due to side effects such as hypotension and bradycardia.

Lofexidine is an alpha-2-adrenergic receptor agonist that was recently approved in the United States for the treatment of opioid withdrawal symptoms. The use of lofexidine as treatment to relieve opioid withdrawal syndrome (OWS) followed the observed benefits of its analog, clonidine, to relieve OWS. There is very limited evidence comparing directly lofexidine to clonidine. Four small controlled studies showed that at the doses that are comparable in relieving acute OWS severity (lofexidine 1.2-1.6 mg/d and clonidine 0.9-1.2 mg/d) patients treated with lofexidine had less hypotensive adverse effects. One study showed that lofexidine was more effective than clonidine in treating or preventing more severe withdrawal during transition onto naltrexone.

Therefore we aim to evaluate the safety and tolerability of lofexidine in the management of opioid withdrawal symptoms while initiating treatment with naltrexone during an outpatient detoxification.

Specific Aims and Hypotheses

Specific Aims and Hypotheses

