The study will be entirely outpatient. Upon study entry, participants will begin clinic visits at the Substance Treatment and Research Service (STARS) clinic. After the detoxification period (2-10 days) where participants will attend the clinic daily, participants will then attend the clinic twice per week for the next 4 weeks and then once per week for the last 4 weeks. All participants will visit the clinic weekly to provide urine toxicology, report on adverse events, and complete additional assessments. All participants will also receive medical management, a medication adherence focused psychosocial intervention that facilitates compliance with study medication and other study procedures, and promotes abstinence from opioids and other substances.

Detoxification and Induction onto Injectable Naltrexone: The detoxification-naltrexone induction will be performed at the STARS outpatient research clinic, which is outfitted with a detoxification suite. After study consent and prior to initiating any study procedures, a urine will be collected and tested for pregnancy. A negative urine pregnancy is required at admission as detoxification and naltrexone treatment would not be recommended during pregnancy.

Participants come to the clinic daily for safety assessments, clinical monitoring, and management of withdrawal. Patients will be seen at the clinic preferably in the morning on Day 1 to initiate the lofexidine-naltrexone procedure. On Study Day 1, following the consent procedure, participants will start lofexidine and will be instructed to begin to abstain from opioids. Vital signs will be checked post 1 hour of initial lofexidine dose to see if there is an effect on blood pressure. Participants will continue to receive lofexidine 0.18mg #3 QID (approximately 9am, 1pm, 5pm, 10pm). Administration of lofexidine is withheld in case of dizziness or lightheadedness complaints, low blood pressure (SBP < 90 or DBP < 60), or orthostatic blood pressure changes (from lying down to standing up drop of SBP \geq 20 mmHg, DBP \geq 10 mmHg). If there are

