Systemic Assessment for Treatment Emergent Events (SAFTEE): The psychiatrist or research nurse queries the patient and logs side effects and other treatment emergent events since the past visit, recording severity, action taken, and whether the side effect(s) is continuing or resolved.

Assessing Medication Compliance: (1) The study psychiatrist during each weekly evaluation queries and records patients' self-reported compliance and missed doses. (2) Compliance is also monitored with pill counts conducted by the research nurse.

Reporting of Adverse Events

All adverse events (AE) reported by the participant or observed by the investigator will be individually listed on the Adverse Event Form (SAFTEE). The signs and symptoms, time of onset, duration, severity, medical intervention, follow-up procedures, and suspected relationship to study drug will be reported. Any AE (clinical signs and symptoms or laboratory test) associated with the use of study drug, whether or not considered drug related, will be documented by the study psychiatrist.

All AEs reports will be reviewed by the study physicians and PI. In the event of any "serious" and/or "unexpected" adverse drug experiences, the PI will notify the Psychiatric Institute IRB and the study sponsor, US WorldMeds.

Please see table of study assessments for complete detail of assessments.

Please attach copies, unless standard instruments are used
study assessments.pdf

Off label and investigational use of drugs/devices

Choose from the following that will be applicable to your study

Research Related Delay to Treatment

Will research procedures result in a delay to treatment?

Yes

Maximum duration of delay to any treatment

Active treatment of known efficacy (induction onto Vivitrol) begins when patients have signed study consent and begin outpatient treatment at STARS. A delay of up to 2 weeks is possible prior to enrollment.

Maximum duration of delay to standard care or treatment of known efficacy

The maximum delay is up to two weeks. Screening, diagnostic and medical evaluation to determine eligibility are generally completed within 3 to 5 days. It may take another week to complete a longer evaluation (for example if input is needed from another treating physician), or for patients to arrange to be

absent from work or family responsibilities. Clinical staff are in regular contact with patients during this time, and patients are informed of other treatment options available in the community.

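### The analysis plan names no summary of vital signs or held lofexidine doses, so symptomless blood-pressure falls reach the safety results only if someone chooses to log them as adverse events.

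*Combined protocol and SAP*

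**What the plan says.** Specific Aims and Hypotheses gives a single aim, the safety and tolerability of lofexidine. Background, Significance and Rationale says of clonidine that "dosing was limited due to side effects such as hypotension and bradycardia", and cites four small controlled studies with less hypotension on lofexidine. The section on side effects and risks of lofexidine lists hypotension first and also names bradycardia.

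Study Procedures sets out the measurements:

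- On Day 1: "Vital signs will be checked post 1 hour of initial lofexidine dose to see if there is an effect on blood pressure".
- During induction: "Evaluation of withdrawal severity (COWS) and vital signs, will be obtained at least twice per day", with daily attendance for 2-10 days.
- At post-detoxification visits: "Vital signs are also taken".

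The same section withholds lofexidine for dizziness or lightheadedness, or for systolic pressure below 90 or diastolic below 60, or for a lying-to-standing fall of at least 20 mmHg systolic or 10 mmHg diastolic. The pressure criteria stand alone and need no complaint. Pressure is repeated after 30 to 60 minutes, and the drug may be held until the next visit.

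On safety, the Overview of Data Analytic Plan says that "non-efficacy outcomes, including retention, frequency of adverse events, and receipt of the first injection of naltrexone-xr will be tabulated and summarized". The other outcomes it names are withdrawal score, opioid use, craving, urine toxicology and depression score.

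**The concern.** A trial that asks whether a drug is tolerable should report the toxicity it most expects, using the measurements it makes for that purpose. Here those measurements are frequent, objective and tied to dosing decisions, yet the analysis plan does not mention them. The only named route by which a pressure fall can reach the safety results is the adverse-event count.

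That route depends on someone deciding that a reading is an event. A participant who crosses a hold limit without feeling unwell, and has a dose withheld, may or may not appear in the table. A withheld dose is itself a tolerability outcome, and the plan does not count it. With no definition fixed in advance, the limit, period and denominator could also be chosen after the data are seen, in an open-label study.

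**Working it through.** The plan states no figure on this point, so there is none to reproduce. The check compares what is collected with what is analysed, and then sizes the gap.

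**Collected against analysed**

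- Blood pressure and other vital signs: collected one hour after the first dose, at least twice per clinic day in induction, and at later visits (Study Procedures). Not named in the analysis plan.
- Lying-to-standing change: a hold criterion in Study Procedures. Not named in the analysis plan.
- Held doses: governed by rule in Study Procedures. Not named in the analysis plan.
- Adverse events: named in the analysis plan, as a frequency.

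**What counts as an adverse event**

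The SAFTEE entry says that the clinician "queries the patient and logs side effects and other treatment emergent events since the past visit". Reporting of Adverse Events goes further: it covers events the investigator observes as well as those the participant reports, and clinical signs as well as symptoms. A low reading found by staff can therefore be logged. Neither section gives a blood-pressure or pulse cut-off, or says that a reading past a hold limit or a held dose must be logged. Capture is permitted but not required.

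**Number of readings in induction**

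Inputs: at least 2 sets per clinic day; 2 to 10 days; 20 participants (projected enrolment).

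- Per participant: 2 × 2 = 4, up to 2 × 10 = 20.
- All 20: 20 × 4 = 80, up to 20 × 20 = 400.

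These are minimum frequencies for participants who attend each day. Early dropout would lower them.

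**How far the adverse-event table could fall short (illustration, assumed rate)**

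The documents give no expected hypotension rate. Suppose 30% of 20 participants, 0.30 × 20 = 6, cross a hold limit, and a share s of them is logged. The expected number in the table is 6 × s:

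| s | expected number shown | of 20 |
|---|---|---|
| 25% | 1.5 | 7.5% |
| 50% | 3 | 15% |
| 75% | 4.5 | 22.5% |
| 100% | 6 | 30% |

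The documents do not fix s, so the shortfall could be anything from none to most of the cases.

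**What the missing table could show**

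Exact (Clopper-Pearson) 95% intervals for the proportion meeting a hold limit:

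- n = 20: 0/20 gives 0 to 16.8%; 2/20 gives 1.2 to 31.7%; 5/20 gives 8.7 to 49.1%.
- n = 10 (the required completers): 0/10 gives 0 to 30.8%; 2/10 gives 2.5 to 55.6%.

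For 0/20 the upper limit is 1 − 0.025^(1/20) = 0.168. The chance of seeing at least one case in 20 is 1 − (1 − p)^20: 64.2%, 87.8% and 98.8% for assumed true rates p of 5%, 10% and 20%. The table would be imprecise but informative.

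**The case against.** Several stronger readings are tempting, and the documents do not support them.

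- *Symptomless falls are missed.* Not necessarily. The hold rule catches them clinically, and the adverse-event section admits observed signs. SAFTEE also records action taken, where a held dose could be entered. What stands is that capture is discretionary.
- *The plan lists every variable to be analysed.* It does not. Its safety list is introduced as non-exhaustive and the section is an overview. But an open list commits to nothing, and craving and depression are named while blood pressure is not.
- *The readings go unused.* They govern whether doses are held and resumed. The gap is in reporting, not in care.
- *Less hypotension is the reason for choosing lofexidine.* It is one reason. The background also cites a study in which lofexidine was more effective than clonidine during transition onto naltrexone. With no clonidine arm, no table could test that comparison here.
- *Adverse events will show half the true rate.* The 15% against 30% contrast is one row of an assumed illustration.

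The practical objections also have force. Twice-daily checks apply to induction only. Heart rate is named explicitly only for the naloxone challenge and is otherwise covered by the general term vital signs. Lying and standing readings are not stated for every check. Visits fall to twice weekly once the taper begins, and clinic visits cannot show every held dose when four doses a day run from about 9am to 10pm. The uploaded assessment table and medication flow chart are not in the text, so they could not be checked. These points limit what the table can contain; they do not remove the case for it.

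**Conclusion.** The point holds in limited form. Followed as written, the analysis plan reports a leading expected toxicity of lofexidine only through adverse events logged at the investigator's discretion, although the protocol requires objective readings that bear directly on the trial's one aim. Adverse-event frequency may therefore understate haemodynamic effects. The size of any understatement is unknown, because the documents give neither a threshold-crossing rate nor a rule that fixes the share logged.

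This should be corrected, but it does not invalidate the trial or suggest that participants are unprotected. The conclusion rests on the text available and assumes that the unseen uploads contain no vital-sign analysis or logging rule.

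**What to change.** Add one descriptive haemodynamic table to the Overview of Data Analytic Plan, limited to readings actually taken. It should run from the first lofexidine dose to the end of induction, plus any visits during the taper.

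For each participant, derive:

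- lowest systolic and lowest diastolic pressure;
- lowest pulse, where recorded;
- change from the pre-dose Day 1 reading;
- largest lying-to-standing fall, where both readings exist.

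Across participants, report:

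- n/N with an exact 95% interval for those meeting each of the protocol's existing hold limits;
- the number of participants, and of clinic visits, with a dose held;
- the number with usable readings for each item.

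The sponsor must first reconcile the hold limits. Study Procedures treats low systolic and low diastolic pressure as alternatives and adds orthostatic criteria. The section on side effects and risks of lofexidine gives one combined 90/60 figure, does not say whether either component suffices, and has no orthostatic criterion. A participant with only the diastolic value below its limit could be counted differently under the two wordings. A sentence saying whether a reading past a limit is to be logged as an adverse event would make the two safety tables interpretable together.

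The cost is a short SAP addition and a check that held doses and body position are recorded. Taper data will be sparse and intervals wide, so the table should be presented as descriptive.
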